6.0	ROL	ROLE OF DATA MANAGEMENT17			
	6.1	Records to Be Kept17			
	6.2	Source Documentation17			
	6.3	Role of Data Management17			
	6.4	Clinical Site Monitoring and Record Availability17			
7.0	ETH	ICAL AND REGULATORY CONSIDERATIONS18			
	7.1	Institutional Review Board (IRB) Review and Informed Consent18			
	7.2	Changes to the Protocol19			
	7.3	Participant Confidentiality19			

	7.4	Study Discontinuation	20
	7.5	Women and Minorities	20
8.0	PUBL	CATION OF RESEARCH FINDINGS	.21
9.0	REFE	RENCES	. 22
APPE	NDIX I	AMC DATA AND SAFETY MONITORING PLAN	.23
APPE	NDIX I	I: SPECIMEN PREPARATION AND SHIPPING INSTRUCTIONS	.27

PROTOCOL ROSTER

AMC Protocol # S004

Clinical and Genomic Factors for Prognosis of Primary Effusion Lymphoma

Protocol Chair:

[name] Moores UCSD Cancer Center [name] [contact] [contact] Email: [contact]

Protocol Co-Chair:

[name], PhD VA San Diego Healthcare System Section of Hematology-Oncology (111E) [name] [contact] [contact] Email: [contact]

AMC Lymphoma Working Group Chair:

[name] [name] Johns Hopkins School of Medicine [name] [contact] [contact] Email: [contact]

Protocol Statistician:

[name] University of Arkansas for Medical Sciences [name] [contact] [contact] Email: [contact]

AMC Biorepository Director:

[name], DA George Washington University Medical Center [name] [contact] [contact] Email: [contact]

Data Management/Operations:

AMC Operations and Data Management Center The Emmes Company [name] [contact] [contact] Email: [contact]

PROTOCOL SYNOPSIS

Title:	Clinical and Genomic Factors for Prognosis of Primary Effusion Lymphoma				
Phase of Study:	Retrospective case series				
Participating Institutions:	This study will be open to participation at all AMC and member institutions				
Accrual Target:	80 participants				
Population:	Participants diagnosed with primary effusion lymphoma (HIV seropositive or negative) on or after January 1, 1998 and on whom survival status at 2 years post diagnosis is available.				
Duration:	Record review and data collection will occur for up to 2 year after the protocol is activated for enrollment of eligible cases.				
Primary Objective:	Objective 1 (Primary clinical objective): Identify baseline clinical characteristics and treatment strategies in patients with AIDS-associated primary effusion lymphoma (PEL) that correlate with long-term survival (≥ 2 years).				
	Objective 2 (Primary genomic objective): Identify differentially expressed genes in PEL that are associated with long-term survival (≥ 2 years).				

1.0 **OBJECTIVES**

1.1 Hypothesis

We hypothesize that there will be a sub-set of PEL clinical characteristics and differentially expressed genes in PEL cells that will be predictive of long-term survival (≥ 2 years), when data from long-term and short-term survivors of the disease are compared.

1.2 Primary Objectives

1.1.1 Primary clinical objective:

Identify baseline clinical characteristics and treatment strategies in patients with AIDS-associated primary effusion lymphoma (PEL) that correlate with long-term survival (≥ 2 years).

1.1.2 Primary genomic objective:

Identify differentially expressed genes in PEL that are associated with long-term survival (≥ 2 years).

2.0 BACKGROUND

2.1 Study Disease

Primary effusion lymphoma (PEL) is a rare type of non-Hodgkin lymphoma (NHL) that presents with predominately body cavity involvement and is nearly universally associated with Kaposi's sarcoma herpesvirus (KSHV), with Epstein Barr virus (EBV) also present in a fraction of cases¹. PEL is typically associated with a poor prognosis with a median survival of 6 months². A solid variant has also been described and carries a similarly poor prognosis³. PEL typically arises in the context of HIV infection, where it accounts for approximately 2-3% of AIDS-NHL².

Data supporting optimal treatment strategies of PEL are limited given the rarity of the disease. There are rare reports of remissions in PEL occurring with the introduction of HAART therapy in HIV patients, who are not on highly active antiretroviral therapy (HAART) at the time of diagnosis. However, HAART is not sufficient for adequate treatment in the vast majority of AIDS-PEL cases. Therefore, combined chemotherapy regimens and other anti-viral treatments are now routinely used for AIDS-PEL treatment. In addition to classic CHOP-based chemotherapy, clinicians and investigators have employed one or more of the following: (a) infusional chemotherapy regimens (EPOCH); (b) methotrexate (after chemotherapeutic debulking or drainage of effusions); (c) VEGF inhibition, aggressive effusion drainage; (d) taken advantage of latent gamma herpes virus tumor infection using bortezomib as an inducer of lytic viral replication and an inhibitor of $NF-kB^4$; and (e) cidofovir or valganciclovir as inhibitors of KSHV replication, with or without interferon⁵. Auto- and allo-geneic hematopoietic stem cell transplant is also reported in the salvage setting with variable success. Long-term AIDS-PEL survivors have been reported², some of whom are being followed at UCSD as well as by collaborators at other institutions within the AMC.

Most of the literature on AIDS-PEL is in the form of single or small case reports, with the largest series including 28 participants reported from a French cohort in 2005^2 . This series explored baseline clinical factors associated with poor survival and identified ECOG performance status > 2 and lack of HAART use at time of diagnosis as independent predictors of shorter survival. A recent review of case in the literature identified the number of body cavity sites as predictive of survival⁶.

An initial genomic evaluation of 9 PEL cases was published by Klein et al., in 2003 and reported PEL as having a distinct profile from other NHLs – including those from immunocompetent and HIV-seropositive hosts – with features of both immunoblasts and plasma cells⁷. Although distinct, AIDS-PEL had a profile most similar to EBV+ immunoblastic diffuse large B cell lymphoma. Despite the limited sample size, they were able to identify 51 genes differentially expressed between PEL cells and normal B cells as well as NHL, including AIDS-NHL.

Past work on gene expression profiling of AIDS-PEL determined that it was quite different from other types of non-HIV and AIDS-related non-Hodgkin's lymphoma⁷ and discerned sub-types of PEL that were primarily associated with the presence, or absence of either KSHV or EBV⁸. In the first study, 9 cases of fresh AIDS-PEL specimens, in the form of cell blocks prepared from cytospins of the PEL fluid, were expression profiled on the Affymetrix U95 GeneChip. Although distinct, AIDS-PEL had a profile most similar to

EBV+ immunoblastic diffuse large B cell lymphoma. Despite the limited sample size, they were able to identify 51 genes differentially expressed between PEL cells and normal B cells as well as NHL, including AIDS-NHL. In the second study, 3 cases of freshly obtained AIDS-PEL mononuclear cells were expression profiled on the Affymetrix U133 GeneChip. In contrast, the intent of this project is to identify genes in PEL, whose expression is associated with long-term survival (≥ 2 years).

Currently, little is known about factors of prognostic importance in PEL. We hypothesize that there will be a sub-set of PEL clinical characteristics and differentially expressed genes in PEL cells that will be of prognostic value for this disease, when data from long-term and short-term survivors of the disease are compared.

2.2 Study Design and Rationale

This is a retrospective analysis to determine the baseline characteristics, treatment patterns and gene expression associated with of long-term survival in HIV-seropositive and negative patients with PEL diagnosed on or after January 1, 1998, a time period during which use of HAART has been widespread in the United States. Due to the rare nature of this disease, data supporting optimal treatment strategies are limited. The AMC is interested in studying this disease because of the disproportional prevalence among people with HIV infection. Information gathered from this retrospective study might serve to initiate future prospective studies in the AMC.

In this study, patient, disease, and treatment information will be obtained from multiple centers within the AMC. Archived biopsy specimens of PEL will also be collected when available for genomics portion of the analysis. The AMC Operations and Data Management Center (AMC ODMC) will provide an electronic clinical research form (CRF) to all participating sites via the AMC AdvantageEDCSM Internet Data Entry System. Each participating AMC center will perform chart reviews after obtaining an Institutional Review Board (IRB) waiver or approval to conduct the study, as determined by the local IRB. All case data will be entered in AdvantageEDC in a de-identified manner, and protected health information (PHI) collected will be limited to information necessary to determine participant eligibility and to address the research questions. Data will be provided to [name]., at the AMC Statistical Center at the University of Arkansas for Medical Sciences for statistical analysis via secure electronic transfer. The data set will only be accessible by the registered investigators, [name] and [name], the statistician, [name], and the AMC ODMC for the purposes of data monitoring and analysis.

3.0 PARTICIPANT SELECTION

Protocol participants must meet all stated eligibility criteria. A rostered AMC investigator must document that each protocol participant meets all stated eligibility criteria Participating sites must have documentation that each eligibility requirement is satisfied prior to participant enrollment. In compliance with CTEP policy, no exceptions to eligibility criteria will be granted in any circumstance.

3.1 Eligibility Criteria

Patients diagnosed with primary effusion lymphoma (HIV seropositive or negative) on or after January 1, 1998 on whom survival status at 2 years post PEL diagnosis is available.

Participants may be enrolled to *either or both* the clinical or genomic portions of the study.

The minimum data required to be able to include a participant for analysis of **clinical prognostic factors** are:

- a. HIV status, and for HIV-positive participants, include CD4 count, HIV viral load within one year prior PEL diagnosis (or within 3 months after PEL diagnosis)
- b. Age at PEL diagnosis
- c. Gender
- d. Stage at PEL diagnosis
- e. Treatment of PEL
- f. Response to PEL treatment
- g. Survival status at 2 years post diagnosis
- h. Pathology slides (or paraffin block) for central review
- i. Year of PEL diagnosis

The minimum data required to be able to include a participant for analysis of **genomic prognostic factors** are:

- a. Availability of a pathologic specimen of PEL that will be submitted for genomic analysis
- b. Survival status at 2 years post diagnosis

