3.2 Exclusion Criteria

Patients who do not fulfill the criteria as listed in Section 3.1 above are ineligible.

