3.3.2 Accrual Rate

An average of 4 participants per month anticipated.

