3.4 Participant Enrollment Procedures

This is a retrospective review. Enrollment is expected to occur over a two-year period. The medical records of participants who meet the inclusion/exclusion criteria will be reviewed. For participants enrolled into the genomics portion of the study, archived pathologic specimens will be obtained. Sites must obtain approval from their Institutional Review Boards (IRB) to waive the requirement for informed consent for this study, or conduct informed consent if required by the local IRB, and register with the AMC ODMC before enrolling participants.

After the investigator at the site has determined that a patient case is eligible for inclusion in this retrospective analysis, the participant will be registered for the protocol on-line via the AMC AdvantageEDCSM Internet Data Entry System. After successful registration, the participant will be assigned a system-generated ten-digit participant ID. Once the eligibility checklist is submitted, a system-generated confirmation email will be sent to the enroller upon successful completion of participant enrollment. If the online system is inaccessible, the site should notify the AMC ODMC (via email at [contact] or via phone at [contact]) for further instructions.

4.0 **RESEARCH METHODS**

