4.2 Study Plan

- 4.2.1 Data, Documents, Records, or Specimen Identification:
 - 4.2.1.1 The following data will be collected for participants enrolled into the clinical portion of the study:
 - HIV status, and for HIV-positive participants, include CD4 count, HIV viral load within one year prior PEL diagnosis (or within 3 months after PEL diagnosis)
 - Age at PEL diagnosis
 - Gender
 - Stage at PEL diagnosis
 - Treatment of PEL
 - Best response to PEL treatment
 - Survival status at 2 years post diagnosis
 - Pathology slides for central review (See Appendix II for specimen preparation and shipping)
 - Year of PEL diagnosis
 - 4.2.1.2 The following will be collected for participants enrolled into the genomics portion of the study:
 - Pathology slides for central review (if unavailable, paraffin block may be submitted)
 - Pathologic specimen that will be submitted for genomic analysis:
 - Frozen specimens, formalin-fixed and paraffin-embedded (FFPE) demonstrating PEL including cytospins as well as any mass/nodal biopsies are acceptable (See Appendix II for specimen preparation and shipping)
 - Survival status at 2 years post diagnosis
 - 4.2.1.3 The following is a list of additional data that is highly desirable for inclusion whenever available for participants enrolled in either the clinical and/or genomics portion of the study:
 - Race and ethnicity
 - For participants with HIV: HIV treatment history (which HAART drugs has participant received prior to PEL diagnosis, after PEL diagnosis), baseline HIV characteristics (i.e., CD4 count and HIV viral load closest

to time of PEL diagnosis, history of opportunistic infections)

- Presence or history of other human herpesvirus-8 (HHV-8)-related diseases (i.e., Kaposi's sarcoma, Multicentric Castleman's Disease), and other malignancies)
- Lymphoma baseline disease characteristics (immunophenotype, Epstein-Barr virus (EBV) and Kaposi sarcoma herpes virus (KSHV) status, sites of extranodal involvement), and either IPI or data required for calculation of International Prognostic Index (IPI)
- Lymphoma treatment: type, number of treatment regimens, use of therapeutic effusion drainage
- Best response to PEL treatment, best response duration
- Survival status at time of enrollment and duration of survival in months from PEL diagnosis

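### Eligibility asks for known 2-year survival status but not that 24 months have passed since diagnosis, so recent cases can enter only as deaths unless the site returns later

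*Combined protocol and SAP*

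**What the plan says.** Section 3.1 takes cases diagnosed "on or after January 1, 1998 on whom survival status at 2 years post PEL diagnosis is available", and the synopsis population entry repeats the condition ("on whom survival status at 2 years post diagnosis is available"). Both minimum-data lists in 3.1, clinical and genomic, include 2-year status. Section 3.2 adds only that "Patients who do not fulfill the criteria as listed" in 3.1 are ineligible. Section 3.0 requires each criterion to be documented before enrollment and says "no exceptions to eligibility criteria will be granted in any circumstance".

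On timing, the synopsis says "Record review and data collection will occur for up to 2 year after the protocol is activated", Section 3.4 says "Enrollment is expected to occur over a two-year period", and Section 3.3.2 gives the rate: "An average of 4 participants per month anticipated". No section states a latest diagnosis date, a minimum elapsed time, a data cut-off or a duty to re-screen patients who are still alive.

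Section 5.1.1 plans Kaplan-Meier estimation and Cox models comparing treatment groups and baseline categories. The time variable that both need, "Survival status at time of enrollment and duration of survival in months from PEL diagnosis", appears only among the additional, desired items in 4.2.1.3. It is not in the minimum data of 3.1.

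**The concern.** Two-year status becomes known at different times for the dead and the living. A death at month 5 settles it at month 5; survival settles it only at month 24. Without a minimum elapsed time, any case reviewed less than 24 months after diagnosis can enter as a death but not as a survivor. Selection then depends on the outcome that Objective 1 and the Cox treatment comparison analyse.

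The affected cases all come from the most recent diagnosis years, so the error does not spread evenly over treatments. It makes regimens used mainly in recent years look worse. Treatment strategies are part of the primary clinical objective, and Section 2.2 expects the results to inform prospective studies. The Kaplan-Meier curve is also pulled down, because recent survivors are left out instead of being censored.

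A separate gap needs no modelling: an eligible case can lack the survival time on which the planned analyses rest.

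**Working it through.** **The plan's own figures.** Section 4.3.1 expects 25-40% long-term survivors: 0.25 × 80 = 20 and 0.40 × 80 = 32, as stated. Section 5.2 gives 15-25%, which is 12 to 20 of 80. At 4 per month (3.3.2), 80 cases are reached in month 80/4 = 20.

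**Inputs.** Median survival is 6 months (2.1). True 2-year survival p is 15%, 25% or 40% (5.2, 4.3.1). The diagnosis window Y is 13 years (3.3) to 19 years (1998 to the 2017 date of the monitoring plan in Appendix I). Even accrual over the window and a Weibull curve are my assumptions.

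**Survival curve.** S(t) = exp(−(t/λ)^k) through S(6) = 0.5 and S(24) = p gives k = ln(ln p / ln 0.5) / ln 4, that is 0.73, 0.50 and 0.20. The mean probability of having died by review, for cases diagnosed in the last 24 months, is a = 1 − (1/24)∫S(t)dt over 0-24 months: 0.620, 0.580 and 0.529.

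**One review, no return.** Let f = 2/Y be the share of cases under 24 months old. Then

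- observed 2-year survival = p(1 − f) / [(1 − f) + f·a]
- deaths-only entries per 80 = 80·f·a / [(1 − f) + f·a]

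For p = 0.25 and Y = 13: f = 0.1538, the denominator is 0.8462 + 0.1538 × 0.580 = 0.9354, observed survival is 0.2115/0.9354 = 22.6%, and deaths-only entries are 80 × 0.0892/0.9354 = 7.6.

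| Site practice | Deaths-only per 80 | True 15% appears as | True 25% appears as |
|---|---|---|---|
| (a) One review, no return; Y = 13-19 | 5-8 | 13.5-14.0% | 22.6-23.4% |
| (b) Sites return until close and also take new diagnoses; Y = 15-21 | 5-7 | 13.7-14.1% | 23.0-23.6% |
| (c) Diagnoses before activation only, half of sites return; Y = 13-19 | 2.5-4 | 14.3-14.5% | 23.9-24.2% |
| (d) As (c), all sites return until month 24 | 0 | 15% | 25% |

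In (a), a true 40% appears as 36.5-37.7%. In (b) the deaths-only band moves to the last 24 months before close. In (d), if enrollment stops at month 20 on reaching 80, patients diagnosed in the last 4 months before activation have not reached 24 months. A true 25% then appears as 24.5-24.7%, with 1.0-1.5 deaths-only entries.

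**Sampling error.** √(p(1 − p)/80) is 4.0 points at 15% and 4.8 points at 25%.

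**Treatment comparison.** Assume a regimen used by 60% of patients in the last 5 years and 20% before. Large simulations under the same survival model give:

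- No true effect: hazard ratio 1.05-1.09 in (a) and (b), 1.03-1.04 in (c), and 1.00 if 24 months are required.
- True hazard ratio 0.70, Y = 15: 0.75-0.78 unstratified, 0.72-0.73 stratified by year of diagnosis, and 0.70 with the 24-month rule.
- With 60 events and 35% exposed, the 95% CI factor is exp(1.96/√(60 × 0.35 × 0.65)) = 1.70 either way.

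**Regimen used only in recent years**, one review, true 25%. Last 5 years (f = 2/5): 0.25 × 0.6/(0.6 + 0.4 × 0.580) = 18%. Last 3 years (f = 2/3): 0.25 × 0.333/(0.333 + 0.667 × 0.580) = 12%. The documents name no such regimen.

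**The case against.** Six points can be made on the other side.

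- **Reading.** Status at 2 years can be taken as a landmark that must have been reached. That would keep early deaths among older cases and remove the problem. But it adds a condition the text does not state, and sites may well read it differently.
- **Time to return.** The two-year window is long enough for every case diagnosed before activation to reach 24 months, and a retrospective study plans no new diagnoses. That is right, and it is why (d) shows no shift. But no section asks sites to wait or return, or bars diagnoses after activation.
- **Size.** The overall shift in (a) is about 0.3 to 0.5 standard errors at a true 25%, and a hazard ratio of 1.09 is small against a CI factor of 1.7. For a regimen confined to the last 5 or 3 years over a 13-year window, at most about 27 or 14 of the 80 would be exposed. Standard errors are then 8 and 11.5 points, so those shifts are only about 0.8 and 1.2 standard errors. All of this stands. Baseline factors unrelated to calendar time are not shown to be affected, and the genomic contrast, which samples 10 long-term and 10 other survivors, is little affected.
- **Assumptions.** Even accrual is assumed, the 19-year window rests on the date of a consortium-wide monitoring plan, and the 40% curve implies about 38% dead within one month. That curve deserves little weight.
- **Remedy.** Year of diagnosis is mandatory, so recent years could be dropped or stratified at analysis. No section plans either. Stratifying removes the bias for a null regimen, still attenuates a real effect, and does not repair the Kaplan-Meier estimate.
- **Partial cancellation.** If 10-20% of deaths go uncaptured (true 25%), the current rule gives 24.5-27.6%, against 27.0-29.4% with the 24-month rule, so the current rule is closer. Under random loss the order reverses: 19.7-22.0% against 21.9-23.5%. The documents cannot say which applies. A chance cancellation of two unmeasured biases is no reason to keep entry that depends on the outcome.

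**Conclusion.** The concern holds as a design weakness that should be corrected, with medium confidence. As written, recent deaths qualify at once and recent survivors do not. The effect on overall 2-year survival is small: with one review and a true value of 15-25%, the loss is 1.0 to 2.4 points, less than sampling error. The effect on treatment comparisons is slight for regimens of mixed use and strong only for one confined to the last few years. It is nevertheless systematic, always against recent regimens, and avoidable before data collection.

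The size rests on even accrual, the Weibull curve through a 6-month median, the assumed usage pattern and site practice, and it falls to zero under full return with diagnoses before activation only. That survival duration is optional while Kaplan-Meier and Cox are planned rests on none of these assumptions.

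**What to change.** 1. In 3.1 and the synopsis, require diagnosis at least 24 months before chart review, or before a fixed cut-off date, whatever the vital status.
2. Move survival duration in months, to death or last contact, from 4.2.1.3 into the clinical minimum data.
3. Keep the primary analysis on cases with known 2-year status. Patients last known alive before 24 months are excluded on any reading. Have sites log them outside the 80, with treatment and months to last contact, and report their number by treatment group.
4. Add the logged patients as censored in a sensitivity analysis only, with all-dead and all-alive bounds. Censoring stays out of the primary analysis because, with 10-20% of deaths uncaptured, it would give 28.0-31.5% for a true 25%. In the loss scenarios examined (10% and 20%, random loss or uncaptured deaths), the bounds contain 25% every time.

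The cost is one eligibility phrase, one required field and a short log. The rule also gives up about 5 to 8 of 80 cases (5/80 = 6% to 8/80 = 10%), a real loss in a rare disease, though all of them are recent deaths whose living counterparts could not enter.

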5.0 STATISTICAL CONSIDERATIONS

5.1 Study Design/Endpoints

5.1.1 Analysis/Statistics

Survival will be estimated using the Kaplan Meier method and Cox proportional hazards model will be used to assess differences between treatment groups and categorical baseline variables. Response rates will be reported with 95% confidence intervals (binomial distribution). Descriptive statistics will be used to summarize baseline clinical, histological, and viral characteristics.

We will perform either RNA-Seq or GeneChip assays, as described in Section 4.3, expression profiling on a total of up to 80 AIDS-PEL specimens. We are already aware of at least 10 long -term AIDS-PEL survivors within the AMC. Resultant data will be assessed for quality, normalized, and then analyzed for differential gene expression. We will use standard algorithms in both GeneSpring and Bioconductor for this purpose, with which we have considerable experience (see Preliminary Studies above). In particular, the RNA-Seq data will be analyzed by the DESeq algorithm in Bioconductor¹. Lastly, we will take advantage of bioinformatic analysis approaches to help make sense of possible biological links between the genes found to be differentially expressed between the sample groups that may be of prognostic significance. These bioinformatic approaches, such as Ingenuity Pathways (http://www.ingenuity.com), focus on the analysis of genetic networks and pathways and help place genes identified as differentially expressed into biologic context.

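### Requiring known 2-year survival status selects, taken alone, against patients lost to follow-up alive, whose time Kaplan-Meier and Cox could use as censored

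*Combined protocol and SAP*

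**What the plan says.** The Population entry of the synopsis restricts the study to patients "on whom survival status at 2 years post diagnosis is available". Section 3.1 states the same condition for the study as a whole: diagnosis "on or after January 1, 1998 on whom survival status at 2 years post PEL diagnosis is available". It then repeats the condition in the minimum data for the clinical analysis, as "g. Survival status at 2 years post diagnosis", and again for the genomic analysis.

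Section 3.2 makes the condition binding: "Patients who do not fulfill the criteria as listed in" Section 3.1 are ineligible. Section 3.0 adds that "no exceptions to eligibility criteria will be granted in any circumstance".

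On analysis, Section 5.1.1 says: "Survival will be estimated using the Kaplan Meier method and Cox proportional hazards model will be used to assess differences between treatment groups". The same sentence applies the Cox model to baseline factors in categories. The section gives no censoring rule. The quantity these methods need, "Survival status at time of enrollment and duration of survival in months from PEL diagnosis", appears in Section 4.2.1.3 among the additional items wanted when available, not in the minimum data.

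**The concern.** The criterion treats two kinds of incomplete follow-up differently. A patient documented as dead at month 6 has a known status at 2 years. A patient in remission who moves to another clinic at month 14 has an unknown status and cannot enter. Among patients whose chart contact would end before 2 years, those seen to die first satisfy the criterion and those last seen alive do not.

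Kaplan-Meier and Cox are built to use the 14 event-free months of the second patient. Leaving them out while keeping the deaths removes time at risk but no events, which lowers estimated survival. If retention differs between the groups compared, for instance by type of centre or by treatment received, the primary clinical comparison of factors and treatments can also be distorted. Usable cases of a rare disease are lost as well: the survey in Section 3.3 found 23 patients at 11 sites over 5 years, against a goal of 80.

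Section 2.2 describes chart review at each centre. The documents describe no tracing or death-registry search that would make 2-year status nearly complete, no count of cases excluded for unknown status, and no sensitivity analysis.

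**Working it through.** **Inputs.** The figure this selection acts on is the expected share of 2-year survivors. Section 4.3.1 gives 25-40%, stated as 20-32 of 80: 80 × 0.25 = 20 and 80 × 0.40 = 32, so it reproduces. Section 5.2 gives 15-25%, which is 12-20 of 80. That the two ranges differ is a separate matter to reconcile; together they bound the true 2-year survival S used here (15-40%). The main example, S = 20%, lies inside the Section 5.2 range. The documents give no loss rate, so every loss figure below is an assumption.

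**Model.** Survival is exponential, and loss among the living is constant and independent of prognosis. With annual loss a:

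- λ = −ln(S)/2 and c = −ln(1 − a), both per year
- A = P(alive and still followed at 2 years) = exp(−2(λ + c)) = S(1 − a)²
- D = P(death seen before loss and before 2 years) = λ/(λ + c) × (1 − A)
- share meeting the criterion = A + D; observed 2-year survival = A/(A + D)

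**Loss per year, S = 20% (λ = 0.805).**

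| Loss per year | Loss by 2 years, 1 − (1 − a)² | A | D | A + D | Ineligible per 80 identified | Observed survival |
|---|---|---|---|---|---|---|
| 10% | 19% | 0.162 | 0.741 | 0.903 | 8 | 17.9% |
| 20% | 36% | 0.128 | 0.683 | 0.811 | 15 | 15.8% |
| 30% | 51% | 0.098 | 0.625 | 0.723 | 22 | 13.6% |

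**Total loss L by 2 years.** Replace (1 − a)² by 1 − L and set c = −ln(1 − L)/2. For S = 20%:

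- L = 5%: A = 0.190, D = 0.785, observed 19.5%
- L = 10%: observed 19.0%
- L = 20%: observed 17.8%
- L = 30%: A = 0.140, D = 0.704, observed 16.6%

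Over L = 5-30%, a true 15% becomes 14.6-12.2%, a true 25% becomes 24.4-21.1%, and a true 40% becomes 39.3-35.1%. The shift is therefore 0.4 to 4.9 points. If deaths after loss are still found, the observed share is S(1 − L)/[S(1 − L) + 1 − S]. A true 25% then becomes 24.1-18.9%, and the largest shift is 8.2 points (40% to 31.8% at L = 30%).

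**Does censoring repair it?** In simulated Kaplan-Meier analyses (n = 200,000, L = 20%), admitting and censoring patients lost alive returns 0.200, 0.250 and 0.399 for true values of 0.20, 0.25 and 0.40. The restricted series returns 0.178, 0.225 and 0.368.

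**Comparisons between groups.**

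- *Unequal loss, no true effect.* With 25% survival in both groups and loss of 5% versus 30% by 2 years, the simulated Cox hazard ratio (n = 20,000) is 1.00 with censoring and 1.12 in the restricted series.
- *Equal loss, no true effect.* With 10% loss in both groups, the hazard ratio is 0.98 in both series. The restriction did not move it; the gap from 1 is simulation error.
- *Equal loss, true effect.* From the Kaplan-Meier figures at L = 20%, the ratio of cumulative hazards at 2 years for 20% versus 40% survival is ln(0.20)/ln(0.40) = 1.76 in truth and ln(0.178)/ln(0.368) = 1.73 in the restricted series, a small change.

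**The case against.** The criterion follows from the stated objectives. The hypothesis and both primary objectives compare survivors of at least 2 years with the rest, and a patient lost at month 14 belongs to neither group. This stands for the binary clinical comparison and for the genomic portion, and known status should be kept there. It does not extend to the Kaplan-Meier and Cox analyses of Section 5.1.1, which do not need a binary status.

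The size rests on assumption, and the upper scenarios are extreme: 30% per year is 51% by 2 years. For scale, the binomial standard error at 20% with 80 patients is √(0.2 × 0.8/80) = 4.5 points, more than the shift of 2.1 points at 10% loss per year or 4.2 points at 20%. If 2-year status is nearly complete, the effect is near zero. All of this stands, although a systematic shift, unlike sampling error, does not shrink with more cases.

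The clinical objective concerns factors, not the level of survival, and comparisons are distorted appreciably only if loss differs between groups. The documents give no evidence that it does, nor that it does not.

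Censoring is not a complete cure. If patients leave care because they are in remission, loss is informative, and Kaplan-Meier and Cox with censoring at last contact are themselves biased. This stands and belongs in the fix.

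A reader might go further and infer that every early death enters, so that the whole series is shown to be tilted toward deaths. The documents do not support this. Section 3.1 also requires response to treatment, stage, CD4 count and viral load for HIV-positive participants, and pathology material for central review. A patient who dies before response is assessed may fail one of these, which selects in the opposite direction. Deaths that go unseen after loss are excluded too.

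**Conclusion.** The point holds for this criterion on its own. As written, it bars patients last known alive before 2 years, while a documented earlier death satisfies it, and the planned time-to-event analyses give no reason for that difference. By itself it pushes estimated survival down. It can bias factor or treatment comparisons where loss differs between groups; with equal loss the hazard ratio changes little.

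The amount cannot be fixed from the documents. For a true 20%, the assumed scenarios run from 19.5% (5% lost in total by 2 years) to 13.6% (51% lost by 2 years). They rest on exponential survival and independent loss. The net direction of selection across all the required items is not established, so the finding should not be read as proof that the final series will understate survival. The change is worth making because it is cheap and recovers cases.

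**What to change.** For the clinical portion:

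- In the synopsis, the opening sentence of Section 3.1 and item g, replace the requirement for known 2-year status with survival time from diagnosis and status (dead, or last known alive) as minimum data. This moves survival duration up from the optional list in Section 4.2.1.3.
- In Section 5.1.1, state that patients lost before 2 years are censored at last contact in Kaplan-Meier and Cox.
- State that this assumes non-informative loss, and add a simple sensitivity analysis, for example treating those lost early first as deaths soon after last contact and then as alive at 2 years.
- Report how many identified cases were lost before 2 years, by the main comparison groups.

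Keep known 2-year status as a requirement for the binary long- versus short-term comparison and for the genomic portion.

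The cost is a wording amendment, with the approvals that Section 7.2 requires, and a case report form change. The dates come from charts already under review. The downside is that some clinical participants will lack a binary 2-year status, so the 2-year proportion is read from the Kaplan-Meier curve and those patients are left out of the binary comparison.
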